**Femoral Peri-arterial Local Anesthetic Injection Decreases Tourniquet Associated
Ischemic Hypertension.**

NCT03390426

Research Summary Version Date: 1/8/2018

Uploaded in Current Form: 10/2/2019

1. Protocol Title:

Femoral Peri-arterial Local Anesthetic Injection Decreases Tourniquet Associated Ischemic Hypertension.

2. Purpose of the Study:

The goal of this prospective randomized double-blind study is to determine if an ultrasound guided peri-arterial injection of local anesthetic around the femoral artery decreases ischemic hypertension associated with prolonged lower extremity tourniquet time. Efficacy will be determined by analyzing incidence of intraoperative ischemic hypertension, defined as $\geq 30\%$ increase in systolic blood pressure, associated with tourniquet inflation times greater than 90 minutes. Secondary outcomes will include post-operative numerical pain scores (NRS 11) and perioperative opioid consumption. English speaking ASA 1-3 patients ages 18-75 years old undergoing total ankle arthroplasty (TKA) will receive both popliteal-sciatic and adductor canal nerve blocks with perineural catheters with 0.2% ropivacaine preoperatively. Patients will then undergo femoral peri-arterial injection with either 1.5% mepivacaine with 1:400,000 epinephrine or 0.9% saline. Data will be analyzed on an intent to treat basis using a two-sided t-test (parametric) or Mann-Whitney-Wilcoxon (non-parametric) with a p -value ≤ 0.05 as significant.

3. Background & Significance:

The use of pneumatic tourniquets to provide a bloodless field is a common technique in orthopedic surgery. Although typically well tolerated initially, prolonged tourniquet duration over 60 minutes often leads to marked increases in both heart rate and blood pressure [1]. This phenomenon has been referred to as tourniquet hypertension. Incidence varies depending on tourniquet time, location, and site of tourniquet [1]. In a retrospective study of 699 patients undergoing surgery with a pneumatic tourniquet, the general anesthesia subgroup had an incidence of 66.7% [2]. Through these studies, tourniquet hypertension has been defined as an increase in either systolic or diastolic blood pressure (SBP or DBP) 30% above baseline.

Etiology of tourniquet hypertension is controversial and not completely understood. Tourniquet pain is thought to arise from uninhibited C fiber activation in the context of decreased inhibition from A- δ fibers. A- δ fibers are inhibited by mechanical compression caused by the tourniquet [3]. Some authors have argued tourniquet pain comes from compression of skin and have shown subcutaneous local infiltration and EMLA cream can improve tolerance of tourniquet [4, 5]. Despite these observations, tourniquet pain and hypertension can be present even with adequate sensory levels during spinal and epidural anesthesia [6]. Another study has shown that combined femoral and proximal sciatic nerve blockade does not reduce incidence of tourniquet hypertension when compared to femoral and popliteal sciatic nerve blocks in surgeries utilizing a below knee tourniquet [7].

A possible reason for tourniquet pain and hypertension despite appropriate peripheral nerve blockade may be due to the location of the sympathetic nerve fiber afferents, including C fibers, which are carried on the femoral artery [8]. For this reason, we propose an injection of local anesthetic between the femoral artery and femoral vein would block perivascular sympathetic nerve fibers. In a small pilot study of 10 patients undergoing TKA who received

periarterial local anesthetic, we found that tourniquet hypertension, which we define as an increase in SBP of 30% above baseline, was prevented in all patients.

4. Design & Procedures:

Preoperatively, patients will be given 975mg acetaminophen by mouth. This medication may be altered or omitted depending on patient comorbidities or extenuating factors such as allergy/intolerance. Study interventions will begin preoperatively. Patients will receive up to 2mg midazolam IV and 100mcg fentanyl IV. As standard of care at Duke Hospital, patients will then undergo ultrasound guided adductor canal and popliteal sciatic peripheral nerve blocks with 20 mL of 0.2% ropivacaine plus insertional of perineural catheters for post-operative analgesia.

ASA 1-3 patients aged 18-75 years old undergoing total ankle arthroplasty or foot fusion will be enrolled. Patients will be identified preoperatively in either preoperative screening clinic or the night prior to surgery depending on method of preoperative screening. Patients in the study will be ASA 1-3 patients, many will be screened by phone instead of a clinic visit. Patients not seen in preoperative screening clinic will be contacted by telephone by primary investigator ([name]) to confirm eligibility and, if eligible and interested, the study will be explained. Patients will be given the opportunity to ask initial questions about the study over the phone. Patients interested in participating will be again have the protocol fully explained and written informed consent will be obtained on the day of surgery prior to receiving any sedation. The patient's care team, including attending surgeons, attending anesthesiologists, residents, and nurse anesthetists will be informed of the patient's inclusion via secure email with specifics for the case.

Inclusion Criteria:

Patients that will be included in the study are English speaking 18-75 year old ASA 1-3 patients undergoing total ankle arthroplasty or ankle fusion procedures.

Exclusion Criteria:

Patients will be excluded from the study if they meet one or more of the following Criteria:

- 1) ASA 4 or 5
- 2) Diagnosis of chronic pain
- 3) Daily chronic opioid use (over 3 months of continuous opioid use).
- 4) Inability to communicate pain scores or need for analgesia.
- 5) Infection at the site of block placement
- 6) Age under 18 years old or greater than 75 years old
- 7) Pregnant women (as determined by point-of-care serum bHCG)
- 8) Intolerance/allergy to local anesthetics
- 9) Weight <50 kg
- 10) Suspected, or known addiction to or abuse of illicit drug(s), prescription medicine(s), or alcohol within the past 2 years.
- 11) Uncontrolled anxiety, schizophrenia, or other psychiatric disorder that, in the opinion of the investigator, may interfere with study assessments or compliance.
- 12) Current or historical evidence of any clinically significant disease or condition that, in the opinion of the investigator, may increase the risk of surgery or complicate the subject's postoperative course.

6. Subject Recruitment & Compensation:

Only patients who are having total ankle arthroplasty or foot fusion are eligible for this study. We will not bias any demographic groups in identifying patients eligible for this study. A total of 30 patients will be consented from Duke University Medical Center. An IRB approved phone script may be used to discuss the study with eligible patients missed at their Pre-Op screening visit. Patients will not receive any additional compensation for enrollment in this study.

7. Consent Process

A patient's permission to be approached for research will be obtained by the primary care team involved with the patient. The consent process will be conducted by the research personnel or one of the physicians involved in the study. The consent process will take place in the pre-operative screening or the surgical clinics. Throughout the consent process, measures will be taken to maintain privacy, such as by conducting face-to-face conversations in private rooms. As much time as necessary will be spent with each potential subject to sufficiently explain and answer all questions, and address all concerns they may have in regard to the study and/or consent process. Under HIPAA waiver, the study team will identify potential subjects from clinic schedules, OR schedules and Maestro Care.

8. Subject's Capacity to Give Legally Effective Consent:

Patients who do not have the capacity to give legally effective consent will not be approached for participation in this study.

9. Study Interventions:

See 4 above.

10. Risk/Benefit Assessment:

Patients will not incur any added risk to standard risks incurred with both general and regional anesthesia. These standards risks are:

- General anesthesia - includes sore throat, hoarseness, injury to teeth, mouth, airway or eye, infection, pneumonia or other lung problem, injury to arteries or veins, allergy or adverse drug reactions, nausea, vomiting, awareness under anesthesia, brain damage, nerve injury or paralysis, and/or loss of life;
- Regional anesthesia - minor pain or discomfort, injury to arteries, veins or nerves affecting the arms or legs, residual numbness or weakness or paralysis, headache, muscle soreness, infection, allergy or adverse drug reaction, intravascular injection of local anesthetic causing seizure or cardiac arrest.

Benefits include contributing to general knowledge base to improve future patient care. This includes potential confirmation of analgesic benefit, improved control of hemodynamics during anesthetic, decreased pain scores, and improved patient satisfaction. Conversely, this study may show no benefit of the block, thereby invalidating the technique.

11. Costs to the Subject:

Subjects will not incur any additional costs to participate in the study. A MaestroCare build will be created to ensure that any subjects are not charged for researched related procedures, equipment, or medications.

12. Data Analysis & Statistical Considerations:

A double blinded randomized trial of 30 subjects (15 per group), assuming a rate of hyperextension of 20% in the placebo group, will provide 82% power to detect a 50% decrease in the rate of tourniquet hypertension in the treatment group in a chi-square test at alpha level 0.05. Sample size and power calculations were performed using PASS v15 (NCSS, LLC. Kaysville, Utah).

Patient and surgical characteristics will be summarized by standard descriptive statistics and will be compared between groups using t-tests, Wilcoxon rank sum tests, chi-square tests, or Fisher exact tests as appropriate. A chi-square test and logistic regression models will be used to assess the effect of treatment on rate of hyperextension. We will report odds ratios, 95% confidence intervals, and p-values to assess significance and clinical importance of the observed treatment effect. Additional measures of treatment efficacy (range of motion, pain scores, and opioid consumption) will be summarized overall and between groups to further characterize the treatment effect in this population. Randomization schedules will be prepared using mixed block sizes in nQuery and significance will be set at 0.05 for all analyses.

13. Data & Safety Monitoring:

In accordance with federal regulations the PI will monitor for, review, and promptly report to the IRB, appropriate institutional officials, sponsor, coordinating center and the appropriate regulatory agency head all unanticipated problems involving risks to subjects or others that occur in the course of a subject's participation in a research study (45 CFR 46.103(b)(5)(i) and 21 CFR 56.108(b)(1)), all AE reports will be reported per the DUHS IRB policies. PI will be monitoring all AEs and submitting reports to the IRB per DUHS IRB policy.

14. Privacy, Data Storage & Confidentiality

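### The stated 82% power is wrong: 15 per group, a 20% placebo rate and a 50% decrease give about 10–11% power

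*Combined protocol and SAP*

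**What the plan says.** Section 12 (Data Analysis & Statistical Considerations) contains the only sample size justification in the document. It describes "A double blinded randomized trial of 30 subjects (15 per group"). The power claim reads "assuming a rate of hyperextension of 20% in the placebo group, will provide 82% power to detect a 50% decrease in the rate"; the decrease refers to tourniquet hypertension in the treated arm, and the power is claimed "in a chi-square test at alpha level 0.05". The calculation is attributed to PASS v15. No treatment-arm rate is given, and no source for the 20%.

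Two other places bear on it. Section 3 (Background & Significance) reports that in a retrospective series "the general anesthesia subgroup had an incidence of 66.7" percent, and Section 4 puts every trial patient under general anesthesia. Section 10 (Risk/Benefit Assessment) says that if the study shows no benefit, the technique would thereby be invalidated.

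**The concern.** A fall from 20% to 10% is a difference of 10 percentage points in a binary outcome, with 3 expected events in one group of 15 and 1.5 in the other. Thirty patients cannot give high power for that. The other reading of a 50% decrease, a drop of 50 percentage points, is impossible from a starting rate of 20%.

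The whole case for N=30 rests on this sentence. A reader who trusts it would take a non-significant result as good evidence that the block does not halve the rate of hypertension. At the written assumptions, a non-significant result is about 90% likely even if the block does exactly that. The remark in Section 10 invites the same misreading.

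**Working it through.** **Inputs (Section 12):** n = 15 per group; placebo rate p1 = 0.20; 50% decrease, so p2 = 0.10; chi-square test; alpha 0.05. I read hyperextension as tourniquet hypertension. Sidedness is not given in the power sentence. I took two-sided, because the chi-square test is two-sided by construction and Section 2 specifies its analysis "using a two-sided t-test (parametric) or Mann-Whitney-Wilcoxon (non-parametric").

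**Formula (pooled normal approximation to the uncorrected chi-square test):**

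power = Φ[(|p1 − p2| − 1.96 × SE0) / SE1], where p̄ = (p1 + p2)/2, SE0 = √[2p̄(1 − p̄)/n] and SE1 = √{[p1(1 − p1) + p2(1 − p2)]/n}.

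**Step 1: the plan's own inputs, 20% versus 10%.**
- SE0 = √(2 × 0.15 × 0.85/15) = 0.1304
- SE1 = √[(0.16 + 0.09)/15] = 0.1291
- power = Φ[(0.10 − 0.2555)/0.1291] = Φ(−1.205) = **11.4%**

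Exact enumeration of all outcomes with the uncorrected chi-square test gives **10.1%**. The stated 82% is not reproduced.

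**Step 2: other ways of calculating the same comparison.**

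| Variant, 20% vs 10% | Power |
|---|---|
| Unpooled variance, two-sided | 11.8% |
| Arcsine, two-sided | 11.8% |
| Noncentral chi-square, N = 30 | 12.0% |
| Fisher's exact test, two-sided | 4.1% |
| Yates-corrected chi-square | 1.9% |
| One-sided, pooled / exact chi-square | 18.8% / 19.7% |
| 30 per group, pooled / exact chi-square | 18.8% / 19.4% |

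None comes near 82%.

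**Step 3: the largest possible benefit from 20%.** Suppose the block prevents every event. With 0 events among 15 treated patients, 3 placebo events give z = 1.83 (not significant) and 4 give z = 2.15 (significant). The exact power is therefore P(at least 4 events in 15 at a rate of 0.20) = **35%**. The normal approximation gives 44%. So with a 20% placebo rate, no benefit of any size gives 82% power with 15 per group.

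**Step 4: the size that the written inputs would need.** n = [1.96√(2 × 0.15 × 0.85) + 0.915√(0.16 + 0.09)]²/0.10² = (0.990 + 0.458)²/0.01 ≈ **210 per group**, 420 in total. For 80% power the figure is 199 per group.

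**Step 5: what does give 82%.**

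| Placebo vs treatment | Pooled | Exact chi-square |
|---|---|---|
| 70% vs 20% | 82.0% | 81.5% |
| 66.7% vs 16.7% | 82.8% | 82.8% |
| 66.7% vs 33.35% (relative halving) | 44.4% | 44.0% |

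For 70% versus 20%: SE0 = √(2 × 0.45 × 0.55/15) = 0.1817; SE1 = √[(0.21 + 0.16)/15] = 0.1571; Φ[(0.50 − 0.3560)/0.1571] = Φ(0.917) = 82.0%. This pair uses the printed 20% and a gap of 50 points. Starting from the 66.7% in Section 3, about 82% requires a fall of 50 points, which is a 75% relative reduction (50/66.7). A relative halving from 66.7% has about 44% power.

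**The case against.** The best defence is that this is a drafting slip: PASS was run correctly on another pair of rates and the sentence misreports them. That is plausible, and it is why the PASS output should be checked first. It does not rescue the sentence, because a 50-point fall is a much larger effect than a halving, and the reader is told the trial can find a halving.

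Several cautions stand.
- The 70% versus 20% reconstruction is a conjecture. No 70% rate appears in the document, and 80% versus 30% gives the same power.
- The 20% is attached to hyperextension, and the same section lists range of motion among the efficacy measures, although Sections 2 and 4 define neither as an outcome. The text may have come from elsewhere, in which case swapping the arms is not the remedy.
- The 66.7% is not a forecast for this control group. Trial patients also receive nerve blocks, Section 3 notes that incidence varies with tourniquet time and site, and the definition there allows either systolic or diastolic pressure, while Section 2 uses systolic only. The 44% is therefore illustrative.
- The Section 10 remark is not a decision rule, and Section 12 promises odds ratios with 95% confidence intervals. What the trial excludes will depend on those intervals. It remains true that at 10% to 44% power, non-significance alone does not exclude a halving.

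**Conclusion.** The concern holds. At the stated inputs the power is about 10–11%, against a stated 82%, an overstatement by a factor of seven to eight. The trial has almost no power for the effect it says it is sized for. The conclusion rests on reading hyperextension as tourniquet hypertension and on a two-sided uncorrected chi-square test. One-sided testing or doubling the groups still leaves power below 20%. The explanation that 20% belongs to the treatment arm and the 50% is absolute is likely but unproven, and the error does not depend on it. The 20% placebo rate also needs justifying beside the 66.7% in Section 3.

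**What to change.** Retrieve the PASS output, then rewrite the sentence in Section 12 so that it names the outcome correctly, gives both arm rates with their source, says whether the reduction is absolute or relative, and states the test and its sidedness.

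- If the output confirms 70% and 20%, suitable text would be: *Assuming tourniquet hypertension in 70% of the placebo group and 20% of the treatment group, an absolute reduction of 50 percentage points, 15 patients per group give 82% power (two-sided chi-square test, alpha 0.05).*
- If another pair was used, state that pair and its power.
- If 20% and a relative halving are truly intended, state the power as about 10%. At N=30 the trial should then not be described as powered for that effect, which would need about 420 patients.

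In every case, add that a non-significant result does not by itself exclude a relative halving and that the confidence interval will be used to judge what is excluded. Soften the Section 10 sentence to match.

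The cost is a rewording in Section 12 and one sentence in Section 10. N stays at 30 and no patients are added. The price is that the detectable effect, honestly stated, is less favourable than the present text suggests.
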